5.5.1. Extent of Exposure

Extent of exposure to GSK3640254 will be summarized.

Duration of exposure in days = Treatment stop date – (Treatment start date) + 1. For Period1 consider oral start date and IV stop date for duration of exposure. Participants who were allocated to treatment but did not report a treatment start date will be categorized as having zero days of exposure. It will be listed.

5.5.2. Adverse Events

Adverse events analyses including the analysis of adverse events (AEs), Serious AEs (SAEs) and other significant AEs will be based on GSK Core Data Standards.

The following categories and subcategories will be used:

- AE

- Any AEs
 - Maximum Grade
- Drug-related AEs
 - Grade
- AEs leading to
 - Permanent discontinuation
 - Withdrawal
- Common AEs
- Common non-serious AEs

- SAE

CONFIDENTIAL

Statistical Analysis Plan 213051

- Any SAEs
 - Grade
- Drug-related SAEs
- Fatal SAEs

Each summary will contain:

- the number of participants with the AE
- the percentage of participants with the AE
- the number of events of the AE

AEs will be displayed by

- Column: Treatment arm or intensity.
- Row: in descending order by SOC and PT, or PT only

A summary of number and percentage of participants with any adverse events by maximum grade will be produced.

The frequency and percentage of AEs (all grades) will be summarized and displayed in two ways: 1) in descending order by PT only and 2) in descending order by SOC and PT.

Adverse events will be coded using the standard Medical Dictionary for Regulatory Affairs (MedDRA dictionary) and graded by the investigator according to the DAIDS (Version 2.1) grading table

5.5.2.1. Adverse Events of Special Interest

The identification and classification of the adverse events of special interest (AESI) will be done programmatically by GSK Biostatistics team.

[Table 8](#) presents the AESI groups. Groups which are not SMQs are made up of a selection of preferred terms (PTs) defined by GSK. The complete list, including the PTs which contribute to each of the groups will be provided by Pharma Safety using the MedDRA version current at the time of reporting.

The summary of event characteristics will be provided for each AESI., including the number of events and occurrences.

Table 8 Adverse Event of Special Interest (AESI)

AESI Group	SMQ	Other
QT prolongation	Torsade de pointes/QT prolongation (SMQ)	Cardiac Disorders SOC; seizures
Gastrointestinal intolerability/toxicity	Narrow ± Broad PTs from three sub-SMQs within the Gastrointestinal nonspecific inflammation and dysfunctional conditions SMQ	
Psychiatric events	Psychosis and psychotic disorders (SMQ; narrow terms); Suicide/self-injury sub-SMQ (narrow terms); Depression (excl suicide and self-injury) sub-SMQ (narrow terms)	Additional PTs for symptoms and complications of Psychiatric events including bipolar disorder, anxiety and sleep disorders
Nervous system disorders		PTs from HLGTS for symptoms and complications of Nervous system disorders
Skin and subcutaneous tissue disorders		Selection of PTs from different HLGTS.

5.5.3. Additional Safety Assessments

The safety data to be summarised are as follows:

Routine laboratory data for haematology, clinical chemistry and urinalysis will be collected, as well as data from additional tests (see Table 6 of the protocol). The key laboratory data to be summarized are as follows:

- Haematology: Platelet Count, red blood cell (RBC) Count, haemoglobin, haematocrit, RBC Indices mean corpuscular volume (MCV), mean corpuscular hemoglobin (MCH) Absolute and %Reticulocytes, WBC count with Differential: Neutrophils, Lymphocytes Monocytes, Eosinophils, Basophils
- Clinical chemistry: Urea Creatinine, Uric acid Fasting glucose etc...

CONFIDENTIAL

Statistical Analysis Plan 213051

- Routine Urinalysis: Routine Urinalysis, pH, glucose, protein, blood, ketones, bilirubin, urobilinogen, nitrite, leukocyte esterase by dipstick
- Microscopic examination (if leukocyte esterase, nitrites, blood or protein is abnormal)
- Screening only Tests: -
 - Alcohol breath test, urine cotinine test
 - Carbon Monoxide (CO) breath test
 - Drug screen (to include at minimum: amphetamines, barbiturates, cocaine, opiates, cannabinoids and benzodiazepines)
 - Serology (HIV antigen/antibody immunoassay, HBsAg, and hepatitis C virus antibody with reflexive HCV RNA)

5.5.3.1. Laboratory Data

Separate summary tables for haematology, and chemistry laboratory tests will be produced. Liver function laboratory tests will be included with chemistry lab tests.

Shift tables of worst-case increase from baseline will be provided for all the laboratory tests and will be used to detect any laboratory parameter clinical important changes:

- For lab test gradable by DAIDS grading table: worst-case grade increase from baseline grade

- For lab tests not gradable by DAIDS grading table, worst-case changes from baseline relative to normal range.

- For urinalysis, worst-case results post-baseline relative to baseline

Summaries of hepatobiliary laboratory events including possible Hy's law cases will be provided in addition to what has been described above. The summary will be produced for worst-case postbaseline only.

5.5.3.2. Vital Signs

Values of vital signs (temperature, systolic and diastolic blood pressure, pulse rate and respiratory rate as well as the change from baseline will be summarized by scheduled visit using mean, median, standard deviation, minimum and maximum.

Shift tables of worst-case results from baseline to potential clinical importance (PCI) criteria will be provided for systolic blood pressure (SBP), diastolic blood pressure (DBP) and heart rate and will be used to detect any clinical important changes.

5.5.3.3. ECG

A 12-lead ECG will be performed at Screening to calculate the heart rate and measurements such as PR, QRS, and QT (uncorrected) intervals. QTcF will be calculated (machine read or manually). ECG after Screening will be performed as clinically indicated.

5.5.3.4. COVID 19 Related Analyses

Based on GSK's "Impact of COVID-19 on Assessment of Safety in Clinical Trials Points to Consider", it is GSK's recommendation that study teams should capture COVID-19 cases based on the WHO criteria using the categories of suspected, probable, and confirmed cases. COVID-19 eCRF pages are used in the study for data collection and analysis purposes. After a discussion with the study team, the following analyses will be included, and summaries will be based on subjects with COVID-19 adverse event:

- Number of subjects with suspected, probable or confirmed for COVID-19 infection
- Number of subjects who had a SARS-COV-2 diagnostic test performed and the number of subjects with positive, negative, or indeterminate results
- Incidence of COVID-19 as reported as an AE and SAE
- Incidence of treatment discontinuation due to SAE or AE of COVID-19 infection
- Severity, duration, and outcome of COVID-19 AEs

Further display details are provided in OPS.

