7.1.5. COVID-19

A participant must permanently discontinue study intervention and be discontinued from the study if they have COVID infection as clinically determined by the investigator (suspect, probable, or confirmed using the most recent version of the WHO case definition) or by laboratory testing.

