3. SAMPLE SIZE DETERMINATION

No formal sample size calculation has been performed for this study. However, the sample size reflects an accepted industry standard for human ADME studies using ¹⁴C radiolabelled drug. Additionally, the design of the study in terms of the concomitant administration of intravenous with oral administration (Period 1) inherently reduces variability in the parameters determined, versus a cross-over design for absolute bioavailability assessment, while enabling cross-over to Period 2 in the same participants. The primary objective of the study is to gain a better understanding of the compound's pharmacokinetic, excretory, and metabolic profile and 4 to 6 participants are deemed sufficient for this purpose. Six participants will be enrolled into the study. To minimize the number of participants exposed to radiation; those participants that discontinue early will not be replaced unless the total number of participants who complete both Periods 1 and 2 drops below 4.

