4. ANALYSIS SETS

Analysis Set	Definition / Criteria	Analyses Evaluated
Screened	
 All participants who were screened for eligibility. This will be the population for reporting screened population data. 	
 Study Population
Enrolled	
 All participants who passed screening and entered the study. Note screening failures (who never passed screening even if rescreened) and participants screened but never enrolled into the study (Reserve, Not Used) are excluded from the Enrolled analysis set as they did not enter the study. 	
 Study Population
Safety	
 All participants who take at least 1 dose of study intervention. Participants will be analysed according to the treatment they received. This will be the population for reporting safety and study population data. 	
 Study / Safety Population
Pharmacokinetic (PK)	
 All participants in the Safety population who had at least 1 non-missing PK assessment (Non-quantifiable [NQ] values will be considered as non-missing values). 	
 PK Population

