In case there is a problem with model convergence, the arithmetic means for \log_e -transformed $AUC_{(0-t)}$ and C_{max} and the treatment differences (85 mg suspension and 200 mg tablet) within each participant will be calculated using only data from the participants who have completed both the periods for 85 mg suspension and 200 mg tablet. The mean treatment difference and paired-t test based 90% CIs for treatment difference in \log_e scale will be estimated. The results will be provided in an exponentially back-transformed scale.

Model Results Presentation

Based on the relative bioavailability, the bioequivalence between 85 mg suspension and 200 mg tablet will be evaluated as follows:

- The bioequivalence is established when the 90% CI of the ratio for $AUC_{(0-t)}$, $AUC_{(0-inf)}$ and C_{max} between treatment formulations (85 mg suspension and 200 mg tablet) are within the range of 0.80 to 1.25.

5.5. (Other) Safety Analyses

The safety analyses will be based on the Safety analysis set, unless otherwise specified.

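### SAP 5.5.3.4 bases every COVID-19 summary on participants who had a COVID-19 adverse event, so the AE incidence is circular and the SAE, discontinuation and testing figures do not describe all dosed participants

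*SAP*

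**What the plan says.** SAP 5.5 sets the default for safety: "The safety analyses will be based on the Safety analysis set, unless otherwise specified". SAP section 4 defines that set as "All participants who take at least 1 dose of study intervention", and SAP section 3 gives the planned size: "Six participants will be enrolled into the study".

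SAP 5.5.3.4 then states a different base for the COVID-19 analyses: "summaries will be based on subjects with COVID-19 adverse event". Five items follow:

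- numbers with suspected, probable or confirmed infection;
- testing, which starts with "Number of subjects who had a SARS-COV-2 diagnostic test performed" and goes on to positive, negative and indeterminate results;
- how often infection was reported as an event, worded as "Incidence of COVID-19 as reported as an AE and SAE";
- how often it ended treatment, worded as "Incidence of treatment discontinuation due to SAE or AE of COVID-19 infection";
- for each COVID-19 AE, its severity, its duration and its outcome.

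The section names no other base and leaves further display detail to the Output and Programming Specification (OPS), which is not among the documents.

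Protocol 7.1.5 bears on the discontinuation item: "A participant must permanently discontinue study intervention and be discontinued from the study if they have COVID infection as clinically determined by the investigator". The same rule covers infection shown by laboratory testing.

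**The concern.** An incidence needs a denominator of participants who could have had the event. Here the base is the set of participants who did have it. For severity, duration and outcome that is right, because those are properties of a case. For AE incidence it makes the percentage uninformative. For SAE and discontinuation incidence it changes the question from what share of dosed men were affected to what share of infected men were affected. For testing it removes the participants most likely to have a negative result.

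Safety and tolerability are a secondary objective. Protocol 6.3 admits the six men on the same day and runs them on the same schedule, and replacement is considered only if completers fall below four. The useful figure is therefore the share of dosed men infected, or lost to treatment, because of COVID-19. A table headed incidence that shows 100% after a single case invites misreading, particularly beside a general AE table that shows 16.7% for the same event.

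**Working it through.** The documents give no COVID-19 rate to reproduce, so the check uses direct proportions.

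**Inputs**
- N = size of the Safety set: 6 planned (SAP section 3). The actual number may differ.
- k = participants with a COVID-19 AE. AEs are collected only from the start of study intervention (Protocol 8.3.1), so these k are all within the Safety set.
- s = those of the k whose COVID-19 event was an SAE.
- d = those of the k who discontinued treatment because of it.

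**1. AE incidence.** As written it is k/k; on the Safety set it is k/N.

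| k | As written | Safety set, N = 6 |
|---|---|---|
| 0 | 0/0, undefined | 0/6 = 0% |
| 1 | 1/1 = 100% | 1/6 = 16.7% |
| 2 | 2/2 = 100% | 2/6 = 33.3% |
| 3 | 3/3 = 100% | 3/6 = 50.0% |

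The as-written column does not depend on N. If the Safety set were 4, one or two cases would be 25.0% or 50.0%. If it were 8, they would be 12.5% or 25.0%.

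**2. SAE incidence.** As written it is s/k, which can lie anywhere from 0% to 100%; on the Safety set it is s/N. With k = 2 and s = 1, that is 1/2 = 50% against 1/6 = 16.7%.

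**3. Treatment discontinuation.** As written it is d/k; on the Safety set it is d/N. With k = 2 and d = 1, it is again 50% against 16.7%. The base does not fix d/k. Protocol 7.1.5 pushes it upward, but only while a dose is still to come.

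- Doses are given on Day 1 of each period, at least 13 days apart.
- After the second dose there are 7 to 14 days of inpatient assessment and then 7 to 14 days to follow-up, so AEs are collected for about 14 to 28 more days.
- With the minimum interval, the share of the AE window before the last dosing day runs from 13/(13 + 28) = 13/41 = 32% to 13/(13 + 14) = 13/27 = 48%.
- If the interval were 20 or 26 days (an assumption), the range would be 20/48 = 42% to 26/40 = 65%.

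A case after the second dose can end study participation but leaves no treatment to stop, so d/k may be well below 100%.

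**4. Testing.** Under the stated base, a participant tested without a COVID-19 AE is in neither the number tested nor the results. Protocol 10.9.3.2 ties the COVID-19 case report form to reported COVID-19 AEs, so the documents do not settle whether such tests would be captured at all.

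**The case against.** The strongest reply is that the sentence does not mention a denominator or a percentage. It may say only which participants feed the display, and the OPS may set the base for percentages. That possibility stands, because the OPS cannot be seen. Against it, the SAP uses the same form of words in 5.2, 5.3, 5.4 and 5.5 to name an analysis population, so reading it that way here follows the SAP's own usage. If the OPS does use another base, the SAP sentence and the OPS disagree and the sentence still needs correcting.

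The second reply is that the overall figures are planned elsewhere, and this also stands. SAP 5.5.2 gives numbers and percentages of participants for each AE, for SAEs, and for AEs leading to permanent discontinuation or withdrawal, on the Safety set by default. Protocol 10.9.3.2 fixes the verbatim terms, so COVID-19 cases can be identified in those tables. SAP 4.1 lists the participants affected by the pandemic and how. A reader might infer that the share of dosed men affected is lost; the documents do not support that. Nor need two percentages on different bases contradict each other, provided each base is labelled.

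A reader might also infer that treatment-discontinuation incidence must come out at or near 100%, given the mandatory stop in Protocol 7.1.5. That goes too far, because the stop can act on treatment only before the second dose. The share of infected participants who discontinued is also a meaningful figure. It is simply not an incidence among dosed participants.

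**Conclusion.** The point holds in a limited form. On the plain reading of SAP 5.5.3.4, COVID-19 AE incidence is circular: always 100% with at least one case and undefined with none. With six dosed participants that is a six-fold overstatement for one case (100/16.7) and three-fold for two (100/33.3). SAE and discontinuation incidence become conditional on infection, and the testing summary is confined to AE cases.

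This rests on two assumptions: that the stated base is the denominator for percentages, and that the planned six are dosed. The first cannot be confirmed without the OPS; the second affects only the size of the contrast.

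The consequence is small. This is a descriptive display in a study with no hypothesis test, and with about six participants the counts can be read directly. The counts of cases are right under either base, and no PK endpoint is touched. It is a desirable correction, not a necessary one.

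**What to change.** In SAP 5.5.3.4, replace the single base with two.

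- **Safety analysis set:** the number with suspected, probable or confirmed infection; AE and SAE incidence; and treatment discontinuation due to COVID-19. Use it for testing as well if tests outside COVID-19 AEs are captured. If they are not, say so and label the testing summary as covering participants with a COVID-19 AE only.
- **Participants with a COVID-19 AE:** severity, duration and outcome only, with that base stated in the display title.

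Align the OPS with the same denominators. The cost is a sentence or so in the SAP and the matching entries in the display specification. The denominator change needs no new data and no protocol amendment. The only drawback is a slightly longer display definition.

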5.6. Interim Analyses

No interim analyses will be performed.

6. SUPPORTING DOCUMENTATION

6.1. Appendix 1 Abbreviations and Trademarks

6.1.1. List of Abbreviations

AE	Adverse Event
ADME	Absorption, distribution, metabolism, and excretion
AMS	Accelerator Mass Spectrometry
AUC(0–inf)	Area under the concentration-time curve from time zero (pre-dose) extrapolated to infinite time
AUC(0–t)	Area under the concentration-time curve from time zero (pre-dose) to last time of quantifiable concentration within a participant across all treatments
BIB	Bioanalysis, Immunogenicity and Biomarkers
BMI	Body mass index
BP	Blood Pressure
C _{max}	Maximum observed concentration
CIOMS	Council for International Organizations of Medical Sciences
CL	Clearance
CL/F	Oral clearance
CL _r	Renal clearance
cm	Centimeter
CRO	Contract research organization
DAIDS	Division of AIDS
DMPK	Drug metabolism and pharmacokinetics
DNA	Deoxyribonucleic acid
ECG	Electrocardiogram
F	Absolute bioavailability
F _a	Fraction absorbed
F _h	Fraction of drug escaping first pass hepatic clearanc
F _g	Fraction of drug escaping gut metabolism
IDSL	Integrated Data Standards Library
IEC	Independent Ethics Committee
IMP	Investigational medicinal product
INR	International normalized ratio
IRB	Institutional Review Board
IV	Intravenous
IVIVT	In vitro / In vivo Translation - Investigative Safety & Drug Metabolism, GSK
kDa	Kilodalton
kg	Kilograms
kg/m ²	Kilograms per meter square

CONFIDENTIAL

Statistical Analysis Plan 213051

LSC	Liquid Scintillation Counting
μSv	Microsievert
MAD	Multiple Ascending Dose
mg	Milligrams
PK	Pharmacokinetic(s)
POC	Proof of concept
QD	Once daily
QTc	Corrected QT interval
QTcF	QT duration corrected for heart rate by Fridericia's formula
QTL	Quality tolerance limit
RNA	Ribonucleic acid
RBC	Red blood cell
SAE	Serious Adverse Event
t_{max}	Time of occurrence of C_{max}
$t_{1/2}$	Terminal phase half-life
TQT	Thorough QT
UK	United Kingdom
ULN	Upper Limit of Normal
VH	ViiV Healthcare group of companies
V_{ss}	Volume of distribution at steady state
V_z/F	Apparent volume of distribution
WHO	World Health Organisation
λ_z	Lambda-z (Terminal Phase Rate Constant)

6.1.2. Trademarks

Trademarks of the GlaxoSmithKline Group of Companies
HARP

Trademarks not owned by the GlaxoSmithKline Group of Companies
SAS

